At Week 52, the subject will undergo testing for primary and secondary efficacy endpoints. Testing for this visit will include an exercise test, an echocardiogram, EndoPAT®, BNP, quality of life questionnaires and safety labs. To minimize any potential effect of the timing of administration of the study drug on testing outcomes, the time of the study drug dosing on the visit day will be standardized. Additionally, if a subject is unable to achieve a maximal effort on exercise testing, they will be offered the opportunity to repeat the EST within two weeks (14 days) of the first test. During this time period, the subject should remain on udenafil. If they achieve a maximal effort on this second study, the results of the second study will be used in the analyses.

At Week 52, vital signs (Resting Blood Pressure/Heart rate) will be obtained; assessment of adverse events, concomitant medications, drug accountability and a blood sample will be drawn for determination of udenafil and metabolite concentration immediately following the exercise test. For female subjects, serum or urine pregnancy test will be administered.

Telephone Contact (Between Baseline and Week 52)

Study coordinators will call each subject the day after drug initiation to ensure the study drug is well tolerated. Subjects will be called at weeks 1, 2, 3, 4, 8, 13, 17, 21, 30, 34, 39, 43, 47 to monitor

adherence, to collect medical history data, and record adverse events through 52 weeks. They will also be called 30 and 90 days after Week 52 to record adverse events. Subjects will be encouraged to notify the study coordinator between scheduled contact dates with any new onset symptoms or complications.

Post-Week 52 Follow-up

Option 1: discontinuation of study drug

If a participant chooses to discontinue study drug after Week 52, a study coordinator will call the subject at 30 (week 56) and 90 days (week 64) to record any additional adverse events possibly or probably related to study drug that may have occurred in the 90 days following completion of the study protocol.

Option 2: continuation of study drug for up to 36 additional months

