Following the Week 52 visit, participants will have the option of continuing on in FUEL-Extension for up to 36 months. During this time, safety data will be collected. Participants will be contacted by the study coordinator on a quarterly basis to monitor and record adverse events. Once study drug has been discontinued (maximum of 36 months following Week 52), subjects will be contacted at 30 days and 90 days following cessation of study drug to monitor for additional adverse events after discontinuation of drug.

For participants who have completed the 24-month extension and have stopped taking study drug for any period of time prior to re-consenting to version 6, the only testing needed prior to re-initiating study drug is a pregnancy test for female participants.

Table 1. Schedule of Events

Visit Number	1	1	TC1	TC 2-15	2	TC 16-17	TC 16 - 28	
Subject Status	New subject (no FUEL)	Former FUEL subject				Post week 52 Option 1	Post Week 52 Option 2	
Time point	Screening/ Baseline Day 0	Screening/ Baseline Day 0	Day 1	Weeks 1, 2, 3, 4, 8, 13, 17, 21, 30, 34, 39, 43, 47	Week 52	Day 30, 90 post-study (Weeks 56 and 64)	Quarterly	Day 30, 90 post-drug discontinue
Visit Window(s)				± 3 days	± 10 days	± 10 days		
Type of Visit(s)	In-Person	In-Person	Call	Calls*	In-Person	Calls	Calls	Calls
Informed Consent/Assent	X	X						
Subject ID# assigned	X							
Inclusion/Exclusion Criteria	X							
Physical Measurements	X							
Medical history	X							
Demographics/expanded demo	X							
Prior/Concomitant Meds	X			X	X			
EndoPAT®	X				X			
Serum or urine pregnancy test	X	X			X			
Clinical Laboratory tests (creatinine, ALT, AST)	X				X			
Biomarker (BNP) sample	X				X			
Genetic repository sample (optional)	X							
Heart Monitor (optional)	X							
Echocardiogram	X				X			
Exercise test (EST)	X ^a				X ^a			
Dispense Open Label Udenafil ^b	X	X						
Resting BP and HR ^c	X	X			X			
Administer first dose of study drug ^c	X	X						
Peds QL generic and cardiac modules; PCQLI; HAES	X				X			
Drug Accountability ^b	X				X			
Pregnancy counseling (if appl)	X	X		X				
Adverse events assessment		X	X	X	X	X	X	X
Morisky Scale (MMAS)				X				
Schedule/Confirm next visit	X	X	X	X	X			

^a If failed 1st exercise test, exercise testing can be repeated w/in 14 days. Pregnancy testing must also be repeated.^b For detailed Drug Accountability procedures, consult the Manual of Operations (MOO)^c For specific timing of procedures, see Additional Procedures and Measurements in Table 2

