6.5 Data Collection

1. Demographic information

The following demographic data will be collected: age, gender, race, ethnicity, cardiac anatomy, date of Fontan, presence of a fenestration, degree of atrioventricular valve regurgitation, grade of ventricular function, concomitant medications, and significant comorbidities.

2. Safety data

Adverse events will be reviewed with each subject at each study visit and during telephone encounters. These events will be recorded and graded by severity and relationship to study drug based on established criteria. Two additional telephone encounters will take place 30 days and 90 days following cessation of study drug [either at Week 52 or up to Week 208 if the subject opts to continue study drug] to assess for any adverse events possibly or probably related to study drug in the period following the completion of study procedures.

3. Exercise stress test

Data from the braked cycle ergometry exercise stress tests will be collected according to protocol established in the PHN Fontan Cross-Sectional Study³.

4. Assessment of ventricular performance

Each study echocardiogram will be stored in a de-identified manner and sent to a core laboratory, which will perform the data analysis and submit the measurements to the PHN Data Coordinating Center (DCC).

5. Vascular function testing

De-identified data from EndoPAT® testing will be collected according to a standardized protocol. These data will be sent to a vascular core lab, which will perform the analysis and submit the measurements to the PHN DCC.

6. Biomarkers

Serum for measurement of BNP level will be sent to a core clinical lab. Results will be sent directly to the PHN DCC.

7. Quality of life survey

Results of the Quality of life surveys will be submitted to the PHN DCC.

8. Samples for the biorepository

Samples collected for the biorepository will be shipped directly to the biorepository for future analysis.

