9. SAFETY ASSESSMENTS

9.1 Safety Considerations and Monitoring

The site study coordinators will contact each subject the day after the baseline visit, then weekly for four weeks and monthly until 52 weeks (12 months), and then at 30 and 90 days from the week 52 visit. If the subject is continuing into the extension of up to an additional 36 months then the site study coordinators will contact each subject quarterly until the subject discontinues study drug. At withdrawal or discontinuation, site study coordinators will contact each subject at 30 and 90 days from withdrawal or discontinuation to record adverse events.

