10. STATISTICS

10.1 Primary Aim - Safety

The primary safety outcome is adverse events. The adverse events will be reported by seriousness, severity and relationship with the study drug. Additionally, the number of subjects experiencing a composite outcome of death, heart failure associated hospitalization, or heart transplant will be reported. The overall assessment of safety will be made on the basis of all available adverse events and safety outcome data over the duration of the 12 months extension trial and an additional 90 days following completion of the study protocol.

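### For participants who stop at Week 52, the last scheduled adverse-event call may fall up to 10 days (16 if Week 64 is read literally) before the 90-day safety period ends

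*Combined protocol and SAP*

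**What the plan says.** Section 6.4 (Post-Week 52 Follow-up, Option 1) states that "a study coordinator will call the subject at 30 (week 56) and 90 days (week 64"). It describes the purpose as recording events with a possible or probable link to the drug "that may have occurred in the 90 days following completion of the study protocol". Table 1 repeats the pairing of days and weeks in its Option 1 column, "Day 30, 90 post-study (Weeks 56 and 64"), and its visit-window row gives that column ±10 days. The Option 2 columns carry no window.

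Section 10.1 bases the overall safety assessment on the 12 months of the extension plus "an additional 90 days following completion of the study protocol".

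The documents use two starting points for the calls:

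- **Week 52.** Section 6.4, under Telephone Contact: "They will also be called 30 and 90 days after Week 52 to record adverse events". The first sentence of section 9.1: "then at 30 and 90 days from the week 52 visit".
- **End of drug.** Section 6.5, item 2: "Two additional telephone encounters will take place 30 days and 90 days following cessation of study drug", with cessation placed at Week 52 or, for those who continue, at up to Week 208. The last sentence of section 9.1 counts from withdrawal or discontinuation. The synopsis, describing the optional extension, refers to three months of follow-up after the last dose.

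The two dates can separate. A participant who does not reach maximal effort at Week 52 may repeat the exercise test within 14 days, and section 6.4 says: "During this time period, the subject should remain on udenafil".

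**The concern.** A telephone call can collect only events that have already happened. If the last planned call may be made before day 90, the days after it belong to the primary safety period but have no planned contact. Adverse events are the primary outcome of this study, and an early call can only miss events in that tail; it cannot add any. How much of the tail is observed would then depend on when each site placed the call.

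The mixed anchors add a second source of variation. Two sites following different sections could start the 90 days on different dates for the same participant.

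**Working it through.** **Inputs**

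- Target of the final Option 1 call: 90 days, also labelled Week 64 (section 6.4 and Table 1).
- Window: ±10 days (Table 1, third entry in the visit-window row, read as belonging to the Option 1 calls).
- Period to be covered: 90 days (sections 6.4 and 10.1).
- Longest time on drug after the Week 52 visit for a repeat exercise test: 14 days (section 6.4).

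Days below are counted from the Week 52 visit, taken as on schedule.

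**Step 1: does Week 64 equal 90 days?** Days after Week 52 = (week label − 52) × 7.

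- Week 56: 4 × 7 = 28, against a stated 30.
- Week 64: 12 × 7 = 84, against a stated 90.

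In the other direction, with Week 52 = 364 days:

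- (364 + 30) / 7 = 56.29
- (364 + 90) / 7 = 64.86

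Rounding would give weeks 56 and 65. Truncation to completed weeks gives 56 and 64, the printed labels. So the labels are either truncated versions of days 30 and 90, or literal targets of days 28 and 84.

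**Step 2: earliest and latest compliant final call**, and the part of the 90 days left after the earliest one.

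| Target | Window | Uncovered at earliest call | Share of 90 days |
|---|---|---|---|
| Day 90 | 80 to 100 | 90 − 80 = 10 days | 11% |
| Week 64 (day 84) | 74 to 94 | 90 − 74 = 16 days | 18% |

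A call made exactly at Week 64 leaves 90 − 84 = 6 days (7%). A call made exactly on day 90 leaves none.

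**Step 3: scale against the whole primary period.** 364 + 90 = 454 days. The uncovered tail is at most 10 / 454 = 2.2%, or 16 / 454 = 3.5% on the literal Week 64 reading.

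**Step 4: anchor.** With no repeat test, Week 52 and cessation coincide for Option 1, as section 6.5 assumes. With a repeat test on drug they differ by up to 14 days.

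**Step 5: a window that closes the gap.** A final call between day 90 and day 100 leaves 90 − 90 = 0 days uncovered.

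**The case against.** The strongest reply is that the target is 90 days wherever it is stated, with the week numbers appearing only in brackets, and that both week numbers fit truncation. That stands. It makes day 80 and 10 days the better-supported figures, with day 74 and 16 days as the outer limit. It does not remove the gap, because ±10 days around day 90 still permits an early call. The window is symmetric, so many calls may fall on or after day 90.

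A reader might go further and infer that adverse-event collection closes at day 74. The documents do not say so. Section 6.4 encourages participants to report between contacts, section 9.2.3 also uses self-report and medical record review, and section 13.2 asks for prompt reporting of serious events. What can end early is the last scheduled enquiry.

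A reader might also infer that a third of the off-drug period is lost: 74 − 14 = 60 days off drug, so 30 of 90 missing. That stacks the literal Week 64 reading, the earliest permitted call, a failed first test, a retest at the full 14 days, and a clock started at the first visit despite section 6.5 and the last sentence of section 9.1. Section 10.1 also counts from completion of the study protocol, not from the end of treatment, and a Week 52 retest can fairly be read as part of that protocol. The 30-day figure is therefore not a fair measure of the problem.

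Finally, the analysis is descriptive, only Option 1 is affected by the stated window, and those who continue have quarterly calls. All of this is true and limits the consequence.

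**Conclusion.** The point holds as a minor one. For Option 1 participants, a fully compliant final call can leave up to 10 days (11%), and at most 16 days (18%), of the 90-day follow-up without scheduled ascertainment. The starting date of those 90 days is stated inconsistently, with a difference of up to 14 days in participants who repeat the Week 52 exercise test on drug.

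This rests on three assumptions: the third window entry in Table 1 applies to the Option 1 calls, the Week 52 visit is on schedule, and no contact follows the final call, since none is scheduled. The documents give no event rate for the last days of the period and no distribution of call dates, so the number of events missed cannot be estimated. Any loss can only lower the count, and it concerns a small part of the total observation time. Nothing here puts the 12-month on-treatment safety data in doubt.

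**What to change.** - In sections 6.4 and 9.1 and in Table 1, count both post-treatment calls from one date: drug cessation, as section 6.5 already does. Section 10.1 should say that its 90 days start from the same date.
- Drop the Week 64 label or correct it so that it agrees with day 90.
- Give the final call a window that opens no earlier than day 90, for example day 90 to day 100, and have it ask about events through day 90.
- State the same window for the Option 2 post-discontinuation calls, which now have none.

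The cost is wording and table entries. No calls are added and treatment is unaffected. The final contact may fall up to about two weeks later than a day-90 count from Week 52 would give, mainly for participants who repeat the exercise test.

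### Section 9.1 promises monthly contact to week 52, but the call list in 6.4 and Table 1 leaves nine weeks (21 to 30) without one and holds 13 calls under a label that counts 14

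*Combined protocol and SAP*

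**What the plan says.** Three places in the protocol set the year-1 contact schedule.

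- **Section 9.1 (Safety Considerations and Monitoring)** gives a rule. Following a Day 1 call, contacts run on this pattern: "then weekly for four weeks and monthly until 52 weeks (12 months), and then at 30 and 90 days from the week 52 visit".
- **Section 6.4 (Telephone Contact, Between Baseline and Week 52)** gives a list, used to check on adherence, medical history and adverse events: "Subjects will be called at weeks 1, 2, 3, 4, 8, 13, 17, 21, 30, 34, 39, 43, 47". The day-after call is stated separately: "Study coordinators will call each subject the day after drug initiation to ensure the study drug is well tolerated".
- **Table 1 (Schedule of Events)** repeats the list as "Weeks 1, 2, 3, 4, 8, 13, 17, 21, 30, 34, 39, 43, 47", with a ±3-day window. Its header numbers the contacts "TC1 TC 2-15 2 TC 16-17 TC 16 - 28". TC1 is the Day 1 call, TC 2-15 is the column holding the listed weeks, and the bare 2 is the in-person Week 52 visit.

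Table 1 has in-person visits only at baseline and Week 52. On how events are found, section 6.5 says: "Adverse events will be reviewed with each subject at each study visit and during telephone encounters". Sections 4.1 and 10.1 make adverse events the primary safety outcome.

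**The concern.** A nine-week interval is not monthly contact, and no visit falls inside it. A site working from 9.1 would call about month 6; a site working from 6.4 or Table 1 would not. In a single-arm study whose primary result is a tabulation of adverse events, the contact schedule is part of how the outcome is measured. If sites can follow different schedules, ascertainment may differ by site, with no control arm against which to judge the difference.

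The same Table 1 column also carries concomitant medications, pregnancy counselling and the Morisky adherence scale, so these share the gap. What is at stake is mainly the milder, self-limited events that depend on a subject's recall, and how soon any problem in mid-year comes to the site's attention.

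**Working it through.** **Inputs.** Listed weeks: 6.4 text and Table 1 (identical). Label TC 2-15, call window of ±3 days and Week 52 window of ±10 days: Table 1. Contact rule: 9.1.

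**1. The plan's own count.**
- Label: 15 − 2 + 1 = 14 calls.
- Listed weeks: 1, 2, 3, 4, 8, 13, 17, 21, 30, 34, 39, 43, 47 = 13 calls.
- With Day 1 as TC1, 13 further calls would end at TC 14, so the label is not reproduced. Day 1 cannot supply the missing one because it has its own column, and Week 52 cannot because it is in-person Visit 2.

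**2. Intervals between consecutive contacts, from week 4 to week 52.**

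| From–to (weeks) | Interval (weeks) |
|---|---|
| 4–8 | 4 |
| 8–13 | 5 |
| 13–17 | 4 |
| 17–21 | 4 |
| **21–30** | **9** |
| 30–34 | 4 |
| 34–39 | 5 |
| 39–43 | 4 |
| 43–47 | 4 |
| 47–52 | 5 |

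**3. Can the windows absorb the gap?**
- Weeks 21 to 30: 9 × 7 = 63 days. Shortest: 63 − 3 − 3 = 57. Longest: 63 + 3 + 3 = 69.
- Longest other interval, weeks 47 to 52, with both windows stretched: 35 + 3 + 10 = 48 days.
- Even at its shortest, the mid-year gap (57 days) exceeds any other interval at its longest (48 days).

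**4. What the 9.1 rule produces.**
- Weekly for four weeks: weeks 1, 2, 3, 4.
- Monthly for months k = 2 to 11, at week floor(52k/12): 8, 13, 17, 21, 26, 30, 34, 39, 43, 47. Month 12 is the Week 52 visit.
- Total: 4 + 10 = 14 calls, equal to the label.
- Compared with the listed weeks, the rule reproduces all 13 and adds one, near week 26. With it, every interval after week 4 is 4 or 5 weeks.
- Rounding to the nearest week instead moves some of the other calls by one week (9, 22, 35 and 48 in place of 8, 21, 34 and 47). It still gives 14 calls, with one at week 26.

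**5. Extra recall time.** Nine weeks against a usual 4 or 5 is 4 to 5 additional weeks, or 4/52 = 7.7% to 5/52 = 9.6% of the year.

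**The case against.** The strongest reply is that the operative schedule is consistent. The explicit week list is the same in 6.4 and Table 1, and the superseded lists in the revision table also have nothing between weeks 21 and 30. On this reading, the 9.1 sentence is a loose summary and TC 2-15 is a slip for TC 2-14. The label is weak evidence on its own: in the same header, TC 16-28 gives 28 − 16 + 1 = 13 numbers for Option 2, while quarterly calls over 36 months (12) plus the 30- and 90-day calls make 14. The asterisk on the call row also has no footnote in the available text, which may be an extraction loss.

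This stands in part. The label cannot prove that a call was dropped. But renumbering would settle only the count; 9.1 would still promise monthly contact that the list does not deliver. A lost footnote would not help either, because 6.4 gives the same weeks with no exception.

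The second reply is that events in the gap are not simply lost. Section 6.4 encourages subjects to report new symptoms between contacts, 9.2.3 allows for events reported to the centre and for record review, and 13.2 asks families to report serious events when they happen. The week-30 call can still record what happened since week 21. Section 8.3 adds bi-monthly pill counts, though returning leftover drug is optional. All of this stands, and it confines the effect to recall and timing.

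A reader might also infer that the gap creates a false mid-year dip in the adverse-event rate that could pass for improving tolerance. The plan does not support this: 10.1 summarises events by seriousness, severity and relationship over the whole 12 months plus 90 days, and plans no display over time.

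**Conclusion.** The contradiction is real and is wrong as written: 13 calls against 14 numbers, and one interval of 63 days (57 to 69) under a rule that promises monthly contact. It matters because these calls are the only scheduled adverse-event ascertainment between baseline and Week 52.

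The consequence is modest: longer recall and later detection around month 6, mainly for milder adverse events, concomitant-medication changes and adherence problems. Deaths, transplants and hospitalizations are unlikely to be forgotten over nine weeks, so the composite in 10.1 should be little affected.

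Two stronger readings should be resisted. One is that a week-26 call was certainly omitted; no document names that week, and it follows only from applying 9.1 to the 4-to-5-week pattern. The other is a percentage of events lost; that would need a forgetting rate and the spread of events over the year, and the documents give neither. The count and intervals rest on no assumption beyond the current text.

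**What to change.** Reconcile 6.4, Table 1 and 9.1 to a single contact list.

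- **Preferred:** add a contact in the week 21 to 30 interval in both 6.4 and Table 1. The list then has 14 calls, the TC 2-15 label is correct, and the monthly ascertainment in 9.1 is delivered. The cost is a small text edit and one extra call per subject, or 300 calls at the 300-subject minimum if all were still to pass that interval.
- **Otherwise:** renumber the calls to match the 13 weeks and reword 9.1 so that it no longer claims monthly contact. This costs text edits only, but leaves the longer recall interval in place.

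Section 6.4 (Option 2) already refers to participants who have completed the 24-month extension, so some subjects are well past this interval. For them, state which schedule was actually followed and report the longer interval alongside the safety results. When correcting the label, check the TC 16-28 numbering in the same header.

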6.5 Data Collection

1. Demographic information

The following demographic data will be collected: age, gender, race, ethnicity, cardiac anatomy, date of Fontan, presence of a fenestration, degree of atrioventricular valve regurgitation, grade of ventricular function, concomitant medications, and significant comorbidities.

2. Safety data

Adverse events will be reviewed with each subject at each study visit and during telephone encounters. These events will be recorded and graded by severity and relationship to study drug based on established criteria. Two additional telephone encounters will take place 30 days and 90 days following cessation of study drug [either at Week 52 or up to Week 208 if the subject opts to continue study drug] to assess for any adverse events possibly or probably related to study drug in the period following the completion of study procedures.

3. Exercise stress test

Data from the braked cycle ergometry exercise stress tests will be collected according to protocol established in the PHN Fontan Cross-Sectional Study³.

4. Assessment of ventricular performance

Each study echocardiogram will be stored in a de-identified manner and sent to a core laboratory, which will perform the data analysis and submit the measurements to the PHN Data Coordinating Center (DCC).

5. Vascular function testing

De-identified data from EndoPAT® testing will be collected according to a standardized protocol. These data will be sent to a vascular core lab, which will perform the analysis and submit the measurements to the PHN DCC.

6. Biomarkers

Serum for measurement of BNP level will be sent to a core clinical lab. Results will be sent directly to the PHN DCC.

7. Quality of life survey

Results of the Quality of life surveys will be submitted to the PHN DCC.

8. Samples for the biorepository

Samples collected for the biorepository will be shipped directly to the biorepository for future analysis.

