6.3 Study Measures

6.3.1 Measures of Primary Aim (Safety)

All adverse events will be collected and recorded for the duration of the trial.

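### Two places limit the 30- and 90-day post-drug calls to adverse events possibly or probably related to study drug; other descriptions of the same calls set no such limit

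*Combined protocol and SAP*

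**What the plan says.** Two places in the current text attach a relatedness qualifier to the calls made 30 and 90 days after study drug stops.

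- Section 6.4, Post-Week 52 Follow-up, Option 1 (subjects who stop at Week 52): the coordinator calls "to record any additional adverse events possibly or probably related to study drug that may have occurred in the 90 days" after completion.
- Section 6.5 item 2, last sentence (subjects who stop at Week 52 or as late as Week 208): the two calls are made "to assess for any adverse events possibly or probably related to study drug in the period following the completion of study procedures".

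Three places describe the same calls without it.

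- Section 6.4, Telephone Contact: "They will also be called 30 and 90 days after Week 52 to record adverse events".
- Section 6.4, Option 2: subjects are "contacted at 30 days and 90 days following cessation of study drug to monitor for additional adverse events after discontinuation of drug".
- Section 9.1: contacts at 30 and 90 days after the Week 52 visit, and after any withdrawal or discontinuation, the latter expressly to record adverse events.

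Section 10.1 breaks the primary safety outcome down by seriousness, severity and relationship to drug. It bases the overall safety assessment on the available data over the 12 months plus a further 90 days.

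On a separate matter, section 6.4 gives 30 days of adverse event follow-up to new subjects removed from drug after the first-dose blood pressure check. Rollover subjects removed at the same step get 90 days, by reference to the FUEL protocol.

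**The concern.** Relationship to drug is one of the three classifications that 10.1 applies to the primary outcome. Under Option 1 as worded, the coordinator judges relatedness during the call and uses that judgement to decide whether an event enters the record. Under the other descriptions, the event is recorded first and its relationship graded afterwards.

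If the restricted wording is followed, the not-related category would be incomplete in the last 90 days of the primary window, while it is collected without restriction during treatment. The related share of recorded events would then rise off drug for a reason that has nothing to do with the drug. An event left out this way also leaves nothing against which the causality judgement could later be checked. The study is single-arm and open-label with safety as its primary aim, so it has no control arm in which the same filter would operate.

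**Working it through.** The plan states no figure on this point, so the check is a comparison of texts.

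**1. Calls after stopping at Week 52.** Telephone Contact and Option 1, both in section 6.4, concern the same two calls, at 30 and 90 days. One records adverse events; the other records those with a possible or probable relation to drug. Section 9.1 agrees with the first.

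**2. Calls after stopping later.** The last sentence of 6.5 item 2 reaches subjects who stop up to Week 208, so it also governs Option 2 subjects. Option 2 itself and 9.1 carry no qualifier.

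**3. General rules.** These do not single out the calls, so they are supporting evidence only, but all point the same way.

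- Section 6.3.1: "All adverse events will be collected and recorded for the duration of the trial".
- Section 6.5 item 2, opening: "Adverse events will be reviewed with each subject at each study visit and during telephone encounters", followed by "These events will be recorded and graded by severity and relationship to study drug based on established criteria". Relationship is graded on events already recorded.
- Table 1: the row "Adverse events assessment" is marked in both post-drug call columns, with no restricting footnote.
- Section 9.2.4: adverse events outside expedited reporting go to the coordinating center within 7 calendar days of first knowledge, with no relatedness condition.

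Take a non-serious, unrelated event mentioned at the 30-day call. It is reportable under 9.2.4 but falls outside what Option 1 says is recorded.

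**4. Which events are exposed.**

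- Possibly or probably related events are captured under every reading.
- Fatal and life-threatening events go to the coordinating center within 24 hours regardless of cause (9.2.4).
- Other serious events have a 24-hour timeframe in the 9.2.4 table without a relatedness condition. The 9.2.4 prose ties that timeframe to events that are unexpected and related. On the prose alone, unrelated serious events fall under the 7-day rule. They have a route either way.
- That leaves mainly non-serious events judged not related, which 9.2.2c defines as clearly due to other factors.

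**5. Size.** Let R and U be the related and unrelated events in the off-drug window, and f the fraction of unrelated events that still reach the record. The recorded related share is R / (R + fU). With f = 1 it is the true share R / (R + U); with f = 0 it is 1. The documents give none of R, U or f, so the distortion cannot be computed.

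**6. First-dose removals (separate point).** The two entry routes differ by 90 − 30 = 60 days. Section 9.1 has contacts at both 30 and 90 days after any withdrawal or discontinuation, so the 30-day statement for new subjects does not agree with it.

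**The case against.** The best defence is that the restriction is partly inferred. Neither sentence contains the word only, and both can be read as giving the purpose of the calls. That is plausible for 6.5, whose verb is to assess. It is weaker for Option 1, whose verb is to record. Nor does it explain why the other descriptions of the same calls omit the phrase.

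A second defence is that Option 1 and 6.5 are deliberate exceptions to a general rule. That could reconcile them with 6.3.1, 9.2.4 and the opening of 6.5 item 2. It cannot reconcile them with Telephone Contact, Option 2 or 9.1, which address these particular calls.

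Third, the analysis is descriptive, with no test, threshold or formal stopping rule attached, and the exposed events are the least informative ones. This stands, and it limits the importance of the point.

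Four stronger readings are tempting but not supported.

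- A reader might infer that deaths or hospitalizations would be missed. The 9.2.4 routes argue against that, despite the disagreement between its table and prose.
- A reader might infer that sites will record differently. That is possible but not shown. Section 12 provides central training, standardized checklists and a study manual, and the forms and manual are not among the documents.
- A reader might take the window's share of follow-up, 90 / (364 + 90) = 19.8% for a subject who stops at Week 52, as the share of data at risk. It is a share of calendar days and says nothing about events lost.
- A reader might say that 10.1 itself requires unrelated events from these calls. It covers the events available, which does not settle what sites must record.

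**Conclusion.** The contradiction is real, it concerns the same calls, and it should be fixed. Option 1 of 6.4 and the last sentence of 6.5 item 2 conflict with Telephone Contact, Option 2 and 9.1, and the general rules favor the unrestricted reading. The consequence is confined to possible under-recording of events judged not related, mainly non-serious ones, in the 90 days after drug stops. Its size is unknown. The conclusion assumes that sites work from the protocol wording; a manual or case report form that already asks for every adverse event would remove the practical effect but not the inconsistency. It does not imply that the capture of drug-related or fatal events is compromised.

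**What to change.** In section 6.4 Option 1 and in the last sentence of section 6.5 item 2, delete the qualifier that confines the events to those with a possible or probable relation to study drug. All adverse events are then recorded at the existing 30- and 90-day calls, and causality is graded afterwards under 9.2.2c. Consistency could also be reached by restricting every passage, but that would cut against 6.3.1 and weaken the breakdown by relationship in 10.1.

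The cost is a wording change in two places and a few more unrelated events to enter and grade. No calls are added.

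As a separate minor correction, the 30-day and 90-day adverse event follow-up statements for subjects removed after the first dose must be reconciled with section 9.1.
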